## 5.5 Study Completion

Study completion will occur at the per protocol defined end of the influenza season but at least 180 days after last vaccination, except for some subjects aged 6 through 11 months at enrollment (see [Time and Events Table](#) and [Section 5.5.2, Countries without MenC market authorization](#)). For all subjects, the study completion visit is a telephone call by a qualified health care professional, or in an exceptional case a clinic or home visit performed by a qualified health care professional.

Subjects aged 6 through 11 months at enrollment, irrespective of treatment allocation, will receive a dose of the MenC vaccine at Visit 5.

The date of study completion is the date of the last contact (clinic or home visit or telephone call) in which the subject's health status was assessed or, in cases where the subject does not agree to any further safety follow-up, it is the date consent is withdrawn. This date should be recorded in the source documents and on the study completion eCRF page. For visit procedures to be performed for a subject whose planned study participation ends prematurely, please see [Section 5.5.1, Early Termination Visit](#).

During the telephone call or clinic/home visit, the following procedures will be performed: Interview of subject's parent(s)/LAR to collect potential: medically-attended AEs within 30 days after the onset of ILI episode, NOCDs, AEs leading to withdrawal, SAEs, ILIs and interview to collect concomitant medications/ vaccinations.

If during the study completion visit, ILI symptoms are reported by the parent/LAR and if the onset of the ILI is within ( $\leq$ ) 6 days before the study completion visit, an NP swab should be collected from the subject for influenza testing and study staff will document the ILI in the subject's source records and on the ILI eCRF (see procedures described in [Section 5.4.2 Unscheduled Visit\(s\)](#)). Should an ILI be identified and a NP swab taken, it is recommended to postpone the study completion visit, to allow for the ILI follow-up visit to occur. In these instances, missing the study completion visit window is not considered a protocol deviation. Should the subject have experienced a protocol defined ILI for which an NP swab was obtained, please collect the information of any medically-attended adverse events which have occurred within 30 days after the onset of the of ILI. If study completion is after the end of influenza season (i.e. after active ILI surveillance), documentation of an ILI and collection of a swab is not applicable.

For subjects who will receive a dose of the MenC vaccine (see [Section 6.2, Vaccine Preparation and Administration](#)) during Visit 5, the vaccine is administered according to the procedures described in [Section 6.2, Vaccine Preparation and Administration](#), and the subject will be observed for at least 30 minutes.

The site will review with the subject's parent(s)/LAR the plan of when information relating to the subject's participation in the study may be available (e.g., study results, treatment assignments). It will also be discussed how information relating to the subject's participation in the study will be shared with the subject's healthcare provider, if the subject's parent(s)/LAR chooses to share this information.

The site will complete the study completion eCRF page and this will mark the completion of the subject's participation in the study.

### **5.5.1 Early Termination Visit**

When a subject is withdrawn from treatment or withdraws from the study, the investigator will notify the Sponsor or Delegate and, when possible, will perform the procedures listed below. The reason(s) for the early termination will be included in the subject's source documentation. If the early termination visit is a telephone call, collect as much information as possible. Early termination visits include subjects who were randomized but not treated.

At the clinic or home visit or during the telephone call, the same procedures will be performed as during the study completion visit, see [Section 5.5, Study Completion](#), if possible. In addition, if applicable, review of subject diary card, collection of subject diary card, interview of subject's parent(s)/LAR to collect: unsolicited adverse events, medically-attended adverse events, NOCDs, AEs leading to withdrawal, SAEs, ILIs, interview of subject's parent(s)/LAR to collect concomitant medications/ vaccinations, blood sampling for immunogenicity. Subject' parent(s)/ LAR of subjects enrolled at the age of 6 through 11 months will be asked to return to the study site at least 6 months after last vaccination to receive a dose of the MenC vaccine. If the subject's parent(s)/LAR is not willing to return, the consequences of not receiving this dose of the MenC- vaccine should be explained and discussions should be documented in the source documentation.

The site will review with the subject's parent(s)/LAR the plan of when information relating to the subject's participation in the study may be available (e.g., study results, treatment assignments). It will also be discussed how information relating to the subject's participation in the study will be shared with the subject's healthcare provider, if the subject's parent(s)/LAR chooses to share this information.

The site will complete the study completion eCRF page and this will mark the completion of the subject's participation in the study.

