### **3.8 Premature Withdrawal from Study**

Subjects may withdraw at any time, or be dropped from the study at the discretion of the investigator should any untoward effects occur and/or for safety reasons. In addition, a subject may be withdrawn by the investigator or the Sponsor if he/she violates the study protocol and related procedures. The investigator or study coordinator must notify the Sponsor immediately when a subject has been withdrawn due to an adverse event.

The circumstances above are referred to as premature withdrawal from the study, and the reason for premature withdrawal should be clearly documented and detailed in the source documentation. The investigator should make every attempt to evaluate the subject's safety, including resolution of ongoing AEs, at the time of premature withdrawal. If a subject want to withdraw from the study before all doses are administered or prior to the last planned study visit, the subject will be asked to be followed for safety for the duration of the study. When a subject withdraws, or is withdrawn, from the study, the procedures described in [Section 5.5.1, Early Termination Visit](#) should be completed if possible.

The reasons for premature withdrawal from the study include: Adverse event, death, withdrawal of consent, lost to follow-up, other, and protocol deviation. These reasons are described in greater detail below.

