## **Adverse Event**

For any subject withdrawn from study participation prior to the planned study completion visit, it is important to determine if an AE was associated with the reason for discontinuing the study. This AE must be identified on the AE eCRF by indicating “Withdrawn from study due to AE”. Any ongoing AEs at the time of study withdrawal must be followed until resolution or stabilization.

Subjects who develop a serious adverse event (SAE) judged to be possibly or probably related to the study vaccine, including hypersensitivity reactions, should not receive subsequent vaccination but the subject will be asked to be followed for safety for the duration of the study.

If a medically-attended adverse event occurred within 30 days following a protocol definition of ILI, the event should also be reported on the AE eCRF page (see [Section 7.1, Safety Assessment](#)).”

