12. Prior vaccination to prevent *Neisseria meningitidis* serogroup C disease or prior infection caused by this organism.
13. Received any other vaccines than influenza vaccine within 14 days (for inactivated vaccines) or 28 days (for live vaccines) prior to study vaccination or who are planning to receive any vaccine within 28 days after study vaccination.

Prior to receipt of second study vaccination, subjects must be evaluated to confirm that they are eligible for subsequent vaccination. If subjects meet any of the original exclusion criteria listed above or experienced severe tolerability issues after first study vaccination, they should not receive additional vaccinations. However, these subjects should be encouraged to continue study participation. This review of eligibility should be documented in the source document and the reason for not administering a scheduled study vaccine should be documented in the eCRF.

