#### **8.4.2.2 Analysis of Primary Efficacy Objective(s)**

##### **8.4.2.2.1 Statistical Hypotheses for Primary Efficacy Objectives**

The primary efficacy analysis will be based on the Full Analysis Set (FAS). Eligible subjects for FAS analysis are subjects who are randomized and received at least one study vaccine, and will be analyzed according to their randomized study vaccine [intent-to-treat analysis]). Absolute vaccine efficacy will only be assessed for RT-PCR confirmed influenza episodes (primary efficacy objective 1a) and culture confirmed influenza

episodes (primary efficacy objective 1b) with first onset of illness occurring at > 14 days after the last vaccination (since clinical protection is not immediate after vaccination) until the end of the influenza season. Additionally, the primary objective will be evaluated in Per-Protocol Analysis Set (PPAS).

Time-to-event methodology based on a proportional hazard model will be used for all efficacy analyses to estimate the hazard ratio (HR). Absolute vaccine efficacy (aVE) against first occurrence RT-PCR confirmed influenza cases will be determined using a standard formula:  $aVE = 1 - HR$  where HR is the hazard ratio for RT-PCR influenza confirmed cases in the QIVc group versus the comparator group. The HR will be estimated by a proportional hazards regression model, described in [Section 8.4.2.2.3, Statistical Methods](#). For which the following null ( $H_0$ ) and alternative ( $H_1$ ) hypotheses will be tested:

$$H_0: 1 - HR \leq 0 \text{ versus } H_1: 1 - HR > 0$$

where HR is a hazard ratio of QIVc versus comparator and VE is vaccine efficacy.

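### Protocol 5.5.1 treats stopping vaccination as leaving the study, contradicting 4.2, 3.8, 5.5 and the ILI surveillance period, so follow-up of children without dose 2 could differ by site

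*Protocol*

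**What the plan says.** Protocol 5.5.1 sets the trigger: "When a subject is withdrawn from treatment or withdraws from the study, the investigator will notify the Sponsor or Delegate". It gives one set of steps for both situations and ends: "The site will complete the study completion eCRF page and this will mark the completion of the subject's participation in the study".

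Other parts of the protocol read differently.

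- Section 4.2 covers children who fail the eligibility re-check before the second vaccination or had severe tolerability problems after the first. They get no further dose. It then says: "However, these subjects should be encouraged to continue study participation". It also requires the reason for the missed dose to be recorded in the eCRF.
- Section 3.8 points to the early-termination steps only on leaving the study: "When a subject withdraws, or is withdrawn, from the study, the procedures described in" Section 5.5.1 are to be completed. Section 5.5 likewise refers there a child whose planned participation ends early.
- Section 3.8, under Adverse Event, says a child with a vaccine-related SAE "should not receive subsequent vaccination but the subject will be asked to be followed for safety for the duration of the study". It does not mention ILI contacts or swabs.
- The List of Definitions runs active ILI surveillance from first vaccination to season end, and Section 5.4.1 runs it weekly from Visit 1 to season end. Neither depends on a second dose.

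On analysis, Protocol 8.4.2.2.1 states: "Eligible subjects for FAS analysis are subjects who are randomized and received at least one study vaccine", and labels this intent-to-treat. SAP 4.4 adds that the child must be evaluated for efficacy more than 14 days after the last vaccination. SAP 6.5.1 right-censors early leavers at the last available eCRF date before season end.

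**The concern.** An intent-to-treat analysis in children with at least one dose needs outcome ascertainment to continue after vaccination stops. Read alone, 5.5.1 ends it. For a two-dose child not given dose 2, the site would file the completion page around Visit 2, and weekly contacts and swabs would cease.

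The grounds for withholding dose 2 include tolerability problems and related SAEs after dose 1. These follow randomization and may differ between QIVc and MenC, so the resulting censoring cannot be presumed non-informative. Because 4.2 points the other way, two sites could handle the same child differently, and the data would not show which reading was followed. What is at stake is the validity of the primary estimate and consistency across sites, not sample size.

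**Working it through.** **1. The passages side by side, for a two-dose child who receives only dose 1**

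| Source | Trigger or scope | Effect on ILI surveillance |
|---|---|---|
| Protocol 5.5.1 | Stops treatment, or leaves study | Ends with the completion page |
| Protocol 4.2 | Not eligible for dose 2 | Continues (child encouraged to stay) |
| Protocol 4.1 | No longer meets inclusion criteria at dose 2 | Not stated |
| Protocol 3.8, Adverse Event | Related SAE | Safety follow-up named; ILI not mentioned |
| Protocol 3.8 and 5.5, pointers to 5.5.1 | Leaves study, or participation ends early | 5.5.1 not triggered by stopping vaccine |
| List of Definitions; Protocol 5.4.1 | First vaccination or Visit 1 to season end | Continues |

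The treatment-withdrawal wording in 5.5.1 is the outlier.

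**2. What a closed-out child contributes**

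The SAP defines last vaccination in two ways.

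- SAP 3.1: the last dose administered in the treatment period. With dose 1 on Day 1, follow-up counts from Day 16 (more than 14 days later). Visit 2 falls on Day 29, window 0 to +7, so Day 29 to 36. Closed out then, the child contributes Day 16–29 (14 days) to Day 16–36 (21 days) and is censored.
- SAP 4.4: Visit 2 for every not previously vaccinated child. Closed out at Visit 2, the child cannot be evaluated more than 14 days after it and may fall out of the FAS.

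**3. The plan's own event counts**

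Inputs (Protocol 8.5): one-sided alpha 0.0125, power 90%, 1:1 allocation, HR 0.60 (1a) and 0.50 (1b). Schoenfeld's formula is d = 4(z₁₋α + z₁₋β)² / (ln HR)², with (2.2414 + 1.2816)² = 12.411.

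- 1a: 4 × 12.411 / 0.2609 = 190.3, so 191. Reproduced.
- 1b: 4 × 12.411 / 0.4805 = 103.3, so 104. Reproduced.

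Power at those counts is 90.1% and 90.2%. It depends on events, so closing children out delays accrual but leaves nominal power at 191 and 104 events unchanged.

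**4. Illustration only**

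The documents give no rate of missed second doses. Assume a share m of evaluable children is closed out after dose 1, contributes no events, and is not already inside the 10% dropout allowance. Expected 1a events at the planned size are 1,487 × 0.08 × 1.6 = 190.3. Multiplying by (1 − m):

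| m | 1a events | Power at fixed N |
|---|---|---|
| 0 | 190.3 | 90.0% |
| 1% | 188.4 | 89.7% |
| 2% | 186.5 | 89.4% |
| 5% | 180.8 | 88.4% |
| 10% | 171.3 | 86.5% |

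For the estimate, suppose one-dose VE is v and full-regimen VE is 40%. Retaining these children gives a mixed VE of about 40% − m(40% − v). Dropping them therefore raises VE by about m(40% − v). At m = 5% that is 1 point for v = 20% and 2 points for v = 0. It is zero if one dose protects fully. For scale, at 191 events and VE 40% the log-HR standard error is 2/√191 = 0.145, and the 97.5% CI for VE is about 17% to 57%.

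Retention can itself cost power. With 5% one-dose children, power at 191 events is 90.1% if one dose gives full VE, 88.0% if half, and 85.6% if none. The case for retention rests on validity.

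**The case against.** The strongest reply is that this is one loose phrase against several consistent passages. Section 4.2 addresses exactly this child and says to encourage continuation, surveillance is defined without reference to dose 2, and 3.8 and 5.5 reserve 5.5.1 for leaving the study. The phrase may have been aimed at children randomized but never vaccinated. Protocol 5.1.4 calls these early terminations, 5.5.1 includes them, and they lie outside the FAS. This stands to a large degree: a reader might infer that the protocol's rule is to drop every child who misses dose 2 from ILI surveillance, and the documents do not support that.

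A reader might also infer that 3.8 limits children with a related SAE to safety follow-up. It is silent on ILI surveillance and does not forbid it, and the 90-day safety call in 5.3.2 includes a question on ILI occurrence.

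Nor do the documents support a specific number of lost cases or a specific VE bias. The share of two-dose children, the missed-dose rate and one-dose efficacy are all absent. Some children miss dose 2 because the family leaves, and no wording would retain them.

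What does not fall away is that 5.5.1 is the operative instruction for closing a child out, and it names treatment withdrawal. Section 4.2 contradicts it without overriding it, and 4.1 withholds vaccination with no sentence on continuing.

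**Conclusion.** The point holds as an internal contradiction that should be reconciled. Section 5.5.1 conflicts with 4.2, with the triggers in 3.8 and 5.5, and with the surveillance period. Depending on which text a site follows, a dose-1-only child either stays under ILI surveillance to season end or is closed out after about two to three weeks of countable follow-up, and under SAP 4.4 may not count at all.

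Confidence is high on the text and low on the size. The figures in the illustration rest on assumed rates and on every affected child being closed out under 5.5.1. No sample-size figure is wrong, and nominal power at 191 and 104 events is unaffected. The risk is informative censoring and a departure from the stated intent-to-treat analysis.

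**What to change.** 1. In Protocol 5.5.1, delete the reference to withdrawal from treatment from the opening sentence and use the trigger in 3.8: the child leaves, or is withdrawn from, the study. Apply the completion page only to those children. The sentence on children randomized but not treated can stay.
2. In 3.8 and 5.5.1, state that a child who receives no further study vaccine but whose consent has not been withdrawn stays in weekly ILI surveillance, swabbing and safety follow-up to season end. This matches 4.2, 5.4.1 and the List of Definitions.
3. In the SAP, reconcile the definitions of last vaccination in 3.1 and 4.4, so that the start of countable follow-up and the FAS membership of a dose-1-only child are clear.

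The cost is a short protocol amendment, a SAP clarification and a note to sites. No new eCRF item is needed, because 4.2 already requires the reason for a missed dose to be recorded. The change concerns follow-up and data collection only and leaves decisions on who is vaccinated untouched.

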### **5.5.2 Countries without MenC market authorization**

In countries where the MenC vaccine is not licensed for use, a Visit 6 for subjects aged 6 through 11 months will be performed, at approximately 28 days after MenC vaccination at Visit 5 (see [Time and Events Table](#)). For these subjects, Visit 6 is the study completion visit. During Visit 6 safety data will be collected (SAE, NOCD, AE leading to withdrawal). Visit 6 may be performed as a telephone call. For all other subjects a Visit 6 is not required.

## 6. TREATMENT OF SUBJECTS

All vaccines associated with this study are to be stored separately from other vaccines and medications in a secure location under appropriate storage conditions with temperature monitoring. All vaccines associated with this study must be checked for expiration date and if it has experienced a temperature deviation prior to use. Expired vaccines or those that have experienced a temperature deviation must not be administered to subjects, as specified in [Section 6.5, Vaccine Supply, Labeling, Storage and Tracking](#).

### 6.1 Study Vaccine(s)

The term ‘study vaccine’ refers to those vaccines provided by the Sponsor, which will be evaluated as part of the study objectives. The study vaccines specific to this study are described below.

#### **Investigational Vaccine:**

**Cell-derived seasonal quadrivalent influenza vaccine:** The investigational vaccine is the cell-derived seasonal quadrivalent influenza vaccine (*Flucelvax Quadrivalent/Flucelvax Tetra*, QIVc, Seqirus).

The *Flucelvax Quadrivalent/Flucelvax Tetra* vaccine is a sterile, slightly opalescent suspension in phosphate buffered saline. The dose to be administered (0.5 mL) is formulated to contain a total of 60 µg hemagglutinin (HA) per 0.5 mL dose in the recommended ratio of 15 µg HA of each of the four (4) influenza strains recommended by WHO for inclusion in the quadrivalent vaccine formulation for the influenza season corresponding to the season of conduct of study. Each dose of *Flucelvax Quadrivalent/Flucelvax Tetra* may contain residual amounts of MDCK cell protein ( $\leq 25.2$  µg), protein other than HA ( $\leq 240$  µg), MDCK cell DNA ( $\leq 10$  ng), polysorbate 80 ( $\leq 1500$  µg), cetyltrimethylammonium bromide ( $\leq 18$  µg), and  $\beta$ -propiolactone ( $< 0.5$  µg), which are used in the manufacturing process. The 0.5 mL pre-filled syringes contain no preservative or antibiotics.

A comprehensive review of the *Flucelvax Quadrivalent/Flucelvax Tetra* vaccine is available in the Investigators Brochure supplied by Seqirus (or delegate). This document should be reviewed by the Investigator prior to initiating the study.

#### **Comparator vaccine(s):**

The comparator is *NeisVac-C* (MenC vaccine, Pfizer Limited), a *Neisseria meningitidis* serogroup C polysaccharide conjugate vaccine. A masking dose of placebo (saline for

injection) will be administered to subjects who required a 2-dose vaccination to maintain the blind in the study.

**Meningococcal (Group C) Conjugate Vaccine:** A dose of 0.5 mL of the *Neisseria meningitidis* serogroup C polysaccharide conjugate vaccine (*NeisVac-C*, Pfizer Limited) will be administered as comparator vaccine.

The *NeisVac-C* vaccine is a sterile, homogenous semi-opaque white to off-white suspension in a single dose syringe. Each dose of 0.5 mL *NeisVac-C* vaccine contains the following active ingredients: 10 µg of meningococcal group C polysaccharide conjugated with 10 to 20 µg of tetanus toxoid protein, adsorbed to aluminium hydroxide (1.4 µg, equivalent to 0.5 µg aluminium), plus the following ingredients: sodium chloride and water (4.1 µg) for injection, Qs to 0.5 mL. *NeisVac-C* vaccine does not contain preservatives or antibacterial agent.

A comprehensive review of the *Neisvac-C* vaccine is available in the Summary of Product Characteristics / Package Insert supplied by Seqirus (or delegate). This document should be reviewed by the Investigator prior to initiating the study.

**Placebo (Saline for injection):** A dose of 0.5 mL of saline for injection (placebo) will be administered as second dose in not-previously influenza vaccinated subjects randomized to the MenC comparator group (see [Table 3.1, Not-previously influenza vaccinated subjects](#)).

Saline for injection is a clear, colorless liquid. Each dose of 0.5 mL saline for injection (placebo) contains the following ingredients: Sodium chloride, 4.5 mg; Water for Injection, Qs to 0.5 mL.

